## Identification of Risk Factors for AEs

For AEs observed within the 24 hour drug administration window, patient's medical history, baseline characteristics and concomitant medications will be reviewed and potential risk factors will be explored.

In addition, the impact of ADA formation on development of hypersensitivity reactions will be evaluated by summarizing the hypersensitivity reactions by ADA status.

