### 3 Study Objectives

The objective of the study is to characterize adverse events (AEs) occurring within 24 hours of TEGSEDI administration in adult patients with hATTR-PN and in individual patients with respect to time course of AE onset, vital sign changes, preventive measures, treatment required, risk factors, and subsequent adverse outcomes.

The endpoints of the study are AEs occurring within the first 24 hours of TEGSEDI administration at study visits, changes in vital signs and cytokines and inflammatory markers 24-hour post-injection with additional assessments of:

- Preventive measures used prior to the injection
- Treatment of AEs post 24 hour injection of TEVESDI at study visits
- Identification of risk factors for AEs occurring within the first 24 hours of TEVESDI administration at study visits
- Correlation of subsequent adverse outcomes

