## 6 Schedule of Assessments

The study will consist of a Screening/Qualification period, a Treatment period and Post-Treatment Follow-up period as per Table 1 and Table 2.

The Screening/Qualification period is defined as the interval of time from the signing of informed consent until the first on-study dose of TEGSEDI.

The treatment period begins at the time of the first on study TEGSEDI administration and the end of treatment period is defined as follows:

- For patients who complete treatment with TEGSEDI on study, the last observation in the treatment period will be the 20-30 hour post-injection visit of the last administered TEGSEDI dose on study. If the time of the last TEGSEDI dose is missing, or the time of the assessment in question is missing, the assessment will be included in the treatment period if it occurred on the same day or one day subsequent to the last dose of TEGSEDI
- For patients who discontinue TEGSEDI or withdraw from the study and continue with TEGSEDI outside the study, the early termination (ET) visit will serve as the end of the treatment period

For patients who discontinue TEGSEDI, the post treatment follow-up period begins after the end of the treatment period, as defined above, and ends with the last available data collected per the clinical trial protocol. Data for the post-treatment follow-up period will be analyzed and summarized separately for patients who develop a hypersensitivity reaction.

	Title: Statistical Analysis Plan				
	Program Name: "A Phase 4 Safety Study Assessing the Adverse Events Occurring Within 24 Hours of TEGSEDI Administration in Patients with polyneuropathy of Hereditary Transthyretin-mediated Amyloidosis (hATTR-PN)"				
	Protocol #: TEG4004				
	[REDACTED]				
	Version: Final 2.0 Effective Date: 06 October 2023				

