### 8.1 Analysis Populations

The safety set includes all patients who received at least one dose of TEGSEDI while enrolled in this study protocol. The safety set will be used in the summary of demographics, medical history, patient disposition, AEs, concomitant medications and ADA (Anti-drug antibody).

The evaluable set includes patients in the safety set having at least one post-dose assessment. The evaluable set will be used in the summaries of AEs by study visit and vital signs and cytokines/inflammatory markers recorded over a 24-hour period.

Listings will be run on the safety set.

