### 8.2.3 Vital Signs

Vital signs include body temperature, heart rate, respiratory rate, and systolic/diastolic blood pressure, and will be summarized using the evaluable set. Observed values and changes from the pre-injection assessment will be calculated for all assessments. Observed values and changes from the pre-injection value will also be calculated by presence/absence of AEs occurring within 24 hours of TEGSEDI administration. For the treatment period, changes will be calculated based on the pre-treatment value of the specific visit. For the post-treatment follow-up period and the early termination visit, changes will be calculated relative to the pre-treatment assessment at Month 0.

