#### 8.2.6 Concomitant Medications

Concomitant medications will be coded using the most recent World Health Organization Drug Dictionary Version and will be updated on re-runs on an ongoing basis. Concomitant medications will be summarized using the safety set by therapeutic/pharmacological subgroup (ATC level 3) and preferred term (ATC Level 5). Concomitant medications given as a preventive measure will be summarized by therapeutic/pharmacological subgroup, preferred term, by treatment month and overall.

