#### 8.2.8 Anti-drug Antibody (ADA) Data

The hypersensitivity reactions will be summarized by ADA status (Yes/No).

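### The SAP looks for risk factors by reviewing patients who had a 24-hour adverse event and describes no comparison with patients who had none

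*Combined protocol and SAP*

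**What the plan says.** SAP section 3 lists among the study's assessments "Identification of risk factors for AEs occurring within the first 24 hours of" dosing at study visits. The method is one sentence in SAP 8.2.2.2, under the risk-factor subheading. It starts from AEs seen in the 24-hour window and says that the patient's "medical history, baseline characteristics and concomitant medications will be reviewed and potential risk factors will be explored". No AE-free group, denominator, statistic or table is named.

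Elsewhere the SAP does make comparisons. For vital signs (8.2.3), "Observed values and changes from the pre-injection value will also be calculated by presence/absence of AEs occurring within 24 hours of TEGSEDI administration", and 8.2.4 treats cytokines and inflammatory markers the same way. For preventive measures, 8.2.2.2 gives the 24-hour AE incidence for injections with and without them, with denominators.

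On anti-drug antibodies (ADA), the risk-factor paragraph adds that "the impact of ADA formation on development of hypersensitivity reactions will be evaluated by summarizing the hypersensitivity reactions by ADA status". Section 8.2.8 repeats this with a Yes/No status and does not say which samples set it.

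**The concern.** To call a characteristic a risk factor, one must know how often it occurs in patients without the event. If only AE patients are reviewed, a trait shared by most of the study population will stand out simply because it is common, and a rarer trait that does raise risk may look unremarkable. History, baseline data and medications are collected for every patient (protocol 9.2.2.1.1 and 9.2.2.1.2; SAP Tables 1 and 2), so the comparison is possible but not described.

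Medications need extra care. Protocol v2.0 section 9.2.4.6 collects them from consent to the End of Study visit, and section 11.4.3.4 has treatments given for an AE recorded there as well, as appropriate. Without a timing rule, a drug given because of the AE can appear among its possible causes.

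**Working it through.** **The plan's own figure.** Protocol 9.4 says that 75 patients give 95% probability of detecting an AE that affects 4% of patients. Check: 1 − 0.96^75 = 0.953, which agrees. The figure concerns seeing at least one case. It does not bear on comparing patients with and without the AE.

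**What a review of AE patients alone can show.** N = 75 comes from the protocol. The other inputs are assumed: 15 patients with a 24-hour AE, 60 without, and the factor in 60% of AE patients (9 of 15). Let c be the number of AE-free patients with the factor.

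- AE risk with the factor = 9 / (9 + c)
- AE risk without the factor = 6 / (6 + 60 − c)
- Risk ratio = the first divided by the second

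| Factor in AE-free patients | c | Risk with factor | Risk without | Risk ratio |
|---|---|---|---|---|
| 30% | 18 | 9/27 = 0.333 | 6/48 = 0.125 | 2.67 |
| 60% | 36 | 9/45 = 0.200 | 6/30 = 0.200 | 1.00 |
| 80% | 48 | 9/57 = 0.158 | 6/18 = 0.333 | 0.47 |

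In all three rows the review sees 9 of 15. The same observation fits a risk factor, a neutral trait or a protective one.

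**Whether other planned tables fill the gap.** Under SAP 8.1, "The safety set will be used in the summary of demographics, medical history, patient disposition, AEs, concomitant medications and ADA", and results are given as n and percent. For a fixed trait, if the count in AE patients is also reported, the rest follows by subtraction.

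- 15 AE patients, 27 of 75 with the trait overall: 27 − 9 = 18 of 60 = 30%.
- 45 AE patients (27 with the trait), 36 of 75 overall: 36 − 27 = 9 of 30 = 30%.

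The full contrast of 60% against 30% is recovered both times. This requires the AE-patient counts, which 8.2.2.2 does not promise. It is exact only where the safety and evaluable sets contain the same patients.

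For medications the subtraction fails. Section 8.2.6 says "Concomitant medications will be summarized using the safety set by therapeutic/pharmacological subgroup" and drug name, without timing relative to the injection. Only preventive medications are broken down by treatment month. If the 9 of 15 include patients given the drug to treat the AE, the resulting contrast partly reflects the AE itself.

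**ADA timing.** For a reaction at a study visit, SAP Table 2 and its footnotes place the Month 0 sample before the reaction. The 20–30 hour, Early Termination and follow-up samples come after it. A reaction at the End of Study visit is an exception, because that visit also has a pre-injection sample. Normally, then, only Month 0 precedes the reaction.

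**The case against.** Four points on the other side have force.

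1. The objective in SAP section 3 covers individual patients as well as the group, so a patient-level review belongs to the study. This stands: the table should be added and should not replace the review.
2. For fixed traits, AE-free counts can be recovered from whole-set tables. A reader might infer that those tables dilute a 30-point contrast to 24 points (60% against 27/75 = 36%) with 15 AE patients, or to 12 points (60% against 36/75 = 48%) with 45. Subtraction undoes that, so dilution is not part of the point. What remains is the missing AE-patient count and, for medications, the missing timing rule.
3. The SAP does not forbid a comparison, and its mock tables (Appendix B) were not available. The SAP also implements protocol v3.0, whereas the protocol supplied is v2.0, so the statements on medication collection rest on v2.0.
4. The study is descriptive and tests no hypothesis. This limits the consequence, but descriptive output is all a reader will have for this assessment.

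On ADA, a reader might infer that the Yes/No table is biased towards linking antibodies with reactions because reactors are sampled more often. The documents do not support this. The bias needs a rule that any positive sample counts, which the SAP never states, and section 6 says "Data for the post-treatment follow-up period will be analyzed and summarized separately for patients who develop a hypersensitivity reaction". The direction is also open. Suppose there is no true effect, samples are independent and positivity is 10% per sample. Three samples in reactors (1 − 0.9³ = 0.271) against two in non-reactors (1 − 0.9² = 0.190) give an odds ratio of (0.271/0.729) / (0.190/0.810) = 1.6. If instead the non-reactors' last sample is positive in 30% (1 − 0.9 × 0.7 = 0.370), it is (0.271/0.729) / (0.370/0.630) = 0.63.

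**Conclusion.** The point holds for medical history, baseline characteristics and concomitant medications: the stated method describes no AE-free comparison and, taken alone, cannot identify a risk factor. It does not extend to vital signs, inflammatory markers or preventive measures, for which the SAP already plans split summaries.

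Under the assumed 15 of 75 patients with an AE and 60% prevalence among them, the same review result fits risk ratios of 1.0 and 2.7. These figures are illustrative and are not predictions for this study. The gap is real for medications, and for fixed traits it is mainly one of presentation. It affects interpretation of a listed assessment, not error rates or sample size, and is worth correcting because it is cheap to do so.

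The ADA wording is a secondary clarification, and the conclusion does not depend on it. The status is undefined in the text supplied, though the mock tables, protocol v3.0 or the protocol's Annex 1 may define it. No direction or size of bias is claimed. Because normally only Month 0 precedes a reaction, the schedule cannot show that ADA formation came first.

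**What to change.** In SAP 8.2.2.2, keep the patient-level review and add an exploratory descriptive table (n, %) in the evaluable set by 24-hour AE yes/no, by visit and overall. Include:

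- demographics, other baseline characteristics and medical history;
- concomitant medications ongoing at that visit's injection, so that drugs given to treat the AE are not counted;
- preventive premedications in separate rows, since they may have been given because of earlier AEs.

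The overall version should state which injection the medication rows refer to. It should also carry a note that patients with more visits have more chances of an AE.

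As a clarification in 8.2.2.2 and 8.2.8, state which samples set ADA status, or cite the definition if the mock tables or protocol v3.0 hold it. Show results from samples taken before and after the reaction separately, and note that normally only Month 0 comes before.

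The cost is SAP wording and some extra descriptive output from data already collected. No new visits, blood draws or assays are needed.

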### 8.2.3 Vital Signs

Vital signs include body temperature, heart rate, respiratory rate, and systolic/diastolic blood pressure, and will be summarized using the evaluable set. Observed values and changes from the pre-injection assessment will be calculated for all assessments. Observed values and changes from the pre-injection value will also be calculated by presence/absence of AEs occurring within 24 hours of TEGSEDI administration. For the treatment period, changes will be calculated based on the pre-treatment value of the specific visit. For the post-treatment follow-up period and the early termination visit, changes will be calculated relative to the pre-treatment assessment at Month 0.

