## 8. Research Question and Endpoints

The objective of the study is to characterize AEs occurring within one day of TEGSEDI administration to adult patients with hATTR-PN overall and in individual patients with respect to time course of AE onset, vital sign changes, preventive measures, treatment required, risk factors, and subsequent adverse outcomes.

The endpoints of the study are the AEs, changes in vital signs and cytokines and inflammatory markers 24-hour post-injection with additional assessments of:

- Preventive measures used prior to the injection
- Treatment of AEs post 24-hour injection
- Identification of risk factors for AEs
- Correlation of subsequent adverse outcomes

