### 9.2.2.1.2. Initial Treatment Visit (Month 0) and Every 4 Months Including End of Study Visit

**Pre-injection assessments** will be performed prior to administration of each dose of TEGSEDI at study visits. Pre-injection assessments will include:

- Abbreviated Physical examination, i.e. weight and vital signs, general appearance, dermatological, respiratory, cardiovascular and abdomen. (except Month 0 if they were performed at Screening)
- Concomitant Medications
- Laboratory testing
  - IgE, IgG, IgM (see [Annex 1](#))
  - Inflammatory markers: C-reactive protein (CRP), Erythrocyte sedimentation rate (ESR), interferon  $\alpha$  (IFN-  $\alpha$ ), IFN- $\beta$ , Chemokines (Macrophage inflammatory protein (MIP)-1a and membrane cofactor protein (MCP)-1), Granulocyte-macrophage colony stimulating factor (GM-CSF), interleukin (IL)-1 $\alpha$ , IL-1 $\beta$ , IL-6, IL-8, IL-12. Tumor necrosis factor –  $\alpha$  (TNF-  $\alpha$ ) (see [Annex 1](#))
  - ADA sampling at Month 0 visit pre-injection first dose and at End of Study visit, pre-injection
  - Urine pregnancy testing for women of childbearing potential
  - Additional blood samples will be drawn and stored for possible future non-genetic testing in this study.
- Adverse events since last study visit

**Post injection assessments** will be made at 1 hour  $\pm$  15 minutes; 2 hour  $\pm$  15 minutes; 4 hour  $\pm$  30 minutes; 8 hour  $\pm$  30 minutes and 20-30 hours following injection of TEGSEDI. Post-injection assessments will include:

- Vital signs
- Laboratory testing
  - IgE, IgG, IgM (see [Annex 1](#))
  - Inflammatory markers: CRP, ESR, IFN- $\alpha$ , IFN- $\beta$ , Chemokines (MIP-1a and MCP-1), GM-CSF, IL-1 $\alpha$ , IL-1 $\beta$ , IL-6, IL-8, IL-12, TNF-  $\alpha$  (see [Annex 1](#))
  - Additional blood samples will be drawn and stored for possible future non-genetic testing in this study
- Adverse events post injection at study visit
- The ADA sample is only drawn post injection, at the 20-30 hour time point, in the event of a hypersensitivity reaction

In addition to these study visits, the patient will be monitored according to the applicable product label.

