## 9.4. Study Size

The study will enroll at least 75 patients.

A sample size of 75 patients will allow 95% probability to detect an AE occurring as infrequently as 4% of patients.

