### **9.6.4. Safety Analysis**

Patient incidence rates of all AEs will be tabulated by Medical Dictionary for Regulatory Activities (MedDRA) system organ class (SOC), and by MedDRA preferred term (PT). Narratives of deaths, all discontinuations, serious AEs, pregnancies and AEs of special interest (AESI) will also be provided.

All treatment emergent AEs, all treatment emergent AEs potentially related to TEGSEDI, all treatment emergent serious AEs, and all treatment emergent serious AEs potentially related to TEGSEDI will be summarized.

Incidence (95% confidence interval) of AEs occurring within 1 day of TEGSEDI administration, and time to onset from TEGSEDI injection and duration of these AEs will be summarized by visit and overall in any visit. The rates of AEs during the 1-day visit occurring after preventive measures will also be summarized. Resolution time with and without treatment administered for the AEs will be summarized.

For each study visit on treatment, the result and change from pre-dose baseline in vital signs (body temperature, heart rate, respiratory rate, and systolic, diastolic blood pressure) and cytokines/inflammatory markers will be summarized using descriptive statistics for all patients in the Evaluable Set and by presence/absence of AEs within 1 day of TEGSEDI administration.

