## 7 Outcome Variables

Outcomes are measured by reported AEs, changes in vital signs and cytokines/inflammatory markers over a 24 hour interval post-injection of TEGSEDI.

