#### 8.2.4 Cytokines and Inflammatory Markers

Cytokines and inflammatory markers include the following parameters: Immunoglobulin (Ig) E, IgG, IgM, C-reactive protein (CRP), Erythrocyte sedimentation rate (ESR), interferon  $\alpha$  (IFN-  $\alpha$ ), IFN- $\beta$ , Chemokines (Macrophage inflammatory protein (MIP)-1a and membrane cofactor protein (MCP)-1), Granulocyte-macrophage colony stimulating factor (GM-CSF), interleukin (IL)-1 $\alpha$ , IL-1 $\beta$ , IL-6, IL-8, IL-12, and Tumor necrosis factor –  $\alpha$  (TNF-  $\alpha$ ). Cytokines and inflammatory markers will be analyzed in the same way as the vital signs using the evaluable set.

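### Vital-sign and marker changes get descriptive statistics only; a worst change per monitored injection, with patient counts where limits can be set, would be a cheap addition

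*Combined protocol and SAP*

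**What the plan says.** SAP section 7 makes these measurements outcomes in their own right: "Outcomes are measured by reported AEs, changes in vital signs and cytokines/inflammatory markers over a 24 hour interval post-injection of TEGSEDI". Under SAP section 3 and protocol section 8, the objective is to characterise AEs in the group and "in individual patients with respect to time course of AE onset, vital sign changes", among other aspects.

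The planned analysis is short:

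- **Vital signs (SAP 8.2.3):** "Observed values and changes from the pre-injection assessment will be calculated for all assessments". The same is repeated by presence or absence of an AE within 24 hours of the injection.
- **Markers (SAP 8.2.4):** "Cytokines and inflammatory markers will be analyzed in the same way as the vital signs using the evaluable set".
- **Protocol 9.6.4:** results and changes from the pre-dose value at each visit "will be summarized using descriptive statistics for all patients in the Evaluable Set and by presence/absence of AEs".
- **Statistics (SAP section 8):** n, mean, SD, SE, median, minimum and maximum for continuous variables. Post-injection changes are taken from the same visit's pre-injection value.

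Protocol 9.2.2.1.2 schedules five post-injection assessments per monitored injection, at 1, 2, 4, 8 and 20-30 hours. None of these sections defines a largest change over the five assessments, a limit for a marked change, a shift table, or a number and percent of patients with such a change.

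**The concern.** An acute reaction to an injection happens in one patient at one hour. If a few patients react, and not all at the same hour, each time-point mean and median is formed almost entirely from patients who did not react. The summaries can then look flat although several patients had large changes. Minimum and maximum show the single most extreme value in a summary. They do not say how many patients changed markedly, or whether the extreme at 2 hours and the extreme at 8 hours belong to the same person.

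At stake is whether the trial can describe acute changes that nobody reported as AEs. For laboratory values this gap is built in: protocol 11.5.1 says that abnormalities judged not clinically significant are not to be reported as AEs. A symptom-free cytokine rise, which the serial sampling is able to detect, would then appear only as a contribution to a group summary.

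**Working it through.** **The plan's own figure.** Protocol 9.4 states: "A sample size of 75 patients will allow 95% probability to detect an AE occurring as infrequently as 4% of patients". Check: 1 - 0.96^75 = 0.953. In reverse, ln(0.05)/ln(0.96) = 73.4, so 74 patients. The figure is reproduced. It is used here only for scale: 4% of 75 is 3 patients. It concerns detecting an AE and is not an expected rate of vital-sign or marker changes.

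**Inputs not in the documents.** The SD of the change and the size of an acute change are assumed: SD 10 to 15 units, and a fall of 30 to 40 units at one assessment only. Values are taken as normal and independent across time points.

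**Effect on a time-point mean, one affected patient of 75.**

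- Shift: 30/75 = 0.40 and 40/75 = 0.53 units.
- SE: 10/√75 = 1.15 and 15/√75 = 1.73 units.
- Ratio of shift to SE:

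| Fall | SD 10 | SD 15 |
|---|---|---|
| 30 | 0.35 | 0.23 |
| 40 | 0.46 | 0.31 |

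Such a shift cannot be told from sampling variation.

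**Effect on the minimum.** Simulation of 5,000 trials of 75 patients and five time points, with one affected patient at each of three time points:

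| SD | Fall | Average minimum without | Average minimum with | Affected patient is the minimum |
|---|---|---|---|---|
| 10 | 30 | -24 | -32 | 71% |
| 10 | 40 | -24 | -40 | 93% |
| 15 | 30 | -36 | -40 | 36% |
| 15 | 40 | -36 | -45 | 60% |

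The minimum does respond, well at SD 10 and less well at SD 15. It still gives no count.

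**What a count would show.** Exact Clopper-Pearson intervals are 0.8% to 11.2% for 3/75 (4.0%) and 2.2% to 14.9% for 5/75 (6.7%). A real count also includes chance crossings. Take an arbitrary 30-unit limit, chosen for arithmetic and not as a clinical proposal, with three patients having a 40-unit fall:

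- SD 10: the expected count rises from 0.5 to 3.0.
- SD 12: the chance of a noise crossing at one assessment is P(Z < -2.5) = 0.0062. Over five assessments, 72 × [1 - (1 - 0.0062)^5] = 2.2 unaffected patients cross. About 2.4 of the 3 affected cross, so the total is about 4.6.
- SD 15: the expected count rises from 8.2 to 10.2.

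The value of a count therefore depends heavily on the limit relative to the measurement noise.

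**The case against.** A reader might infer that acute changes are averaged away and never counted. The documents do not support that.

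- **Extremes are reported.** SAP section 8 includes the minimum and maximum, and the simulation shows that they often pick up the affected patient.
- **The AE split links the two endpoints.** The objective is worded around AEs, with vital-sign change as one aspect of them, and the split addresses that directly. In a small AE-present group dilution is much weaker: with 10 such patients (assumed), one 40-unit fall moves the mean by 40/10 = 4 units.
- **The AE route counts.** Protocol 11.3.1 allows any unfavourable sign to be an AE, so a marked blood-pressure fall can be reported. SAP 8.2.2.2 would then count it by visit and overall with a 95% interval. The exclusion in protocol 11.5.1 concerns laboratory values, not vital signs. SAP 8.2.5 also counts patients with hypersensitivity at each visit.
- **The table layout is not visible.** Separate displays at each time point are inferred from the wording of SAP 8.2.3. The mock tables in Appendix B are cited but their content is not available, and SAP 8.1 mentions listings without saying which. The SAP also refers to protocol version 3.0, whereas the protocol reviewed is version 2.0.
- **A worst-of-five value has its own bias.** It lies away from zero even if the drug does nothing, and no control arm shows by how much.

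All of this stands, and it limits the point. What remains is narrower. The AE route depends on the investigator's judgement, and the AE split is still a group summary, with unreported changes falling in the AE-absent group. Neither the minimum nor the maximum gives a count or follows a patient across the series.

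**Conclusion.** The point holds as a cheap improvement, not as a defect that undermines the study. The visible text plans no per-injection worst change and no number of patients with a marked change for two named outcomes. What escapes is confined to changes not reported as AEs, and mainly to marker changes judged not clinically significant.

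The illustrated dilution, 0.23 to 0.46 SE for one affected patient of 75, rests on assumed SDs, assumed fall sizes and a change confined to one assessment. The documents do not say how often such changes occur or at what hour they peak. Nor should a reader expect a threshold table to show exactly 3/75 when three patients react: at SD 12 with the illustrative limit, nearly half of the roughly 4.6 patients counted would be noise. If the mock tables already contain a worst-change display, the point reduces to naming it in the SAP text.

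**What to change.** In SAP 8.2.3 and 8.2.4, for each monitored injection, derive the largest rise and the largest fall from the same-visit pre-injection value over the 1, 2, 4, 8 and 20-30 hour assessments. Summarise both as continuous variables, by visit and by presence or absence of a 24-hour AE. This form needs no cut-off.

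For vital signs, and for markers only where the sponsor can set limits before database lock, add the number and percent of patients beyond those limits, with Clopper-Pearson intervals, the method that SAP section 8 already names.

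State the limits of reading in the SAP: a worst-of-five value is biased away from zero, there is no control arm, and some crossings are measurement noise. The counts are therefore descriptive and should be read against the AE-absent group. That group is a reference, not a control, because a marked change may itself be what was reported as the AE.

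The cost is one set of derived variables and one table per parameter group, with no new data. Agreeing limits is the larger task. SAP 8.2.3 and 8.2.4 name 5 vital-sign measures and 16 markers, so limits in both directions for all of them would mean (5 + 16) × 2 = 42. That is why the marker counts should be optional.
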